# 8.2.3 Expectedness

Adverse Events can be Expected or Unexpected.

An expected adverse event is an event previously known or anticipated to result from participation in the research study or any underlying disease, disorder, or condition of the subject. The event is usually listed in the Investigator Brochure, consent form or research protocol.

**An unexpected adverse event** is an adverse event not previously known or anticipated to result from the research study or any underlying disease, disorder, or condition of the subject.

#### 8.2.4 Attribution

Attribution is the relationship between an adverse event or serious adverse event and the study drug. Attribution will be assigned as follows:

- Definite The AE is clearly related to the study drug.
- Probable The AE is likely related to the study drug.
- Possible The AE may be related to the study drug.
- Unlikely The AE is doubtfully related to the study drug.
- Unrelated The AE is clearly NOT related to the study drug.

# 8.3 Reporting Procedures for All Adverse Events

All participating investigators will assess the occurrence of AEs throughout the subject's participation in the study, beginning at the time of initiation of treatment. Subjects will be followed for toxicity for 30 days after treatment has been discontinued or until death, whichever occurs first. The clinical course of each event will be followed until resolution, stabilization, or until it has been determined that the study treatment or participation is not the cause.

The investigator is responsible for ensuring that all adverse events observed by the investigator or reported by the subject which occur after the subject has initiated treatment are fully recorded in the subject's case report form, subject's medical records, and/or any other institutional requirement. Source documentation must be available to support all adverse events.

A laboratory test abnormality considered clinically relevant (e.g., causing the subject to withdraw from the study), requiring treatment or causing apparent clinical manifestations, or judged relevant by the investigator, should be reported as an adverse event.

The investigator will provide the following for all adverse events:

- Description of the event
- Date of onset and resolution
- Grade of toxicity
- Attribution of relatedness to the investigational agent
- Action taken as a result of the event
- Outcome of event

In this study, descriptions and grading scales found in the NCI Common Terminology Criteria for Adverse Events (CTCAE) version 4.03 will be utilized for AE reporting, available at: http://evs.nci.nih.gov/ftp1/CTCAE/CTCAE 4.03 2010-06-14 QuickReference 8.5x11.pdf

Investigative sites will report adverse events to their respective IRB according to the local IRB's policies and procedures in reporting adverse events.

# 8.4 Serious Adverse Event Reporting Procedures

Serious adverse events that occur beginning with initiation of treatment, during treatment, or within 30 days of the last dose of treatment must be reported to the MD Anderson Cancer Center Principal Investigator.

Investigative sites will report serious adverse events to their respective IRB according to the local IRB's policies and procedures in reporting serious adverse events.

# 8.4.1 Pfizer Reporting

The Investigator Initiated Research Serious Adverse Event Form provided by Pfizer will be utilized for reporting all SAEs to Pfizer.

#### 9.0 PHARMACEUTICAL INFORMATION

A list of the adverse events and potential risks associated with the investigational or commercial agents administered in this study can be found in Section 8.0.

#### Sunitinib

Chemical Name: 5-(5-fluoro-2-oxo-1,2-dihydro-indol-(3Z)-ylidenemethyl)-2,4-

dimethyl-1H-pyrrole-3-carboxylic acid(2-diethylamino-ethyl)-

amide; compound with (S)-2-hydroxy-succinic acid.

Other Names: SUNITINIB L-Malate salt; SU010398; PHA-290940AD; Sutent;

SUNITINIB, sunitinib malate

Classification: Receptor tyrosine kinase inhibitor (RTK)

**Molecular Formula:**  $C_{22}H_{27}FN_4O_2.C_4H_6O_5$ 

**Mode of Action:** Sunitinib malate is a receptor tyrosine kinase inhibitor involved

in tumor proliferation and angiogenesis, specifically inhibiting platelet derived growth factor receptor, vascular endothelial growth factor receptor, stem cell factor receptor, Fms-like

tyrosine kinase-3 receptor, and ret proto-oncogene.

Metabolism: Cytochrome P450 (CYP) 3A-mediated N-deethylation to form

SU012662 was the major pathway of the metabolism of sunitinib in liver microsomes from rats, monkeys, and humans. Sunitinib metabolism was predominately mediated by CYP3A4 and produced an active metabolite, SU012662. This metabolite and sunitinib were the only major drug-related compounds found in systemic circulation in mice, rats, monkeys, and humans. Minor metabolites of sunitinib were mainly found in excreta and were either not found or found at very low levels in plasma. Sunitinib and SU012662 were not potent inducers or inhibitors of major CYP450 enzymes. The efflux transporters, P-gp and BCRP, did

not appear to play a significant role in the pharmacokinetics of sunitinib. Therefore, sunitinib and SU012662 are predicted to have a low potential to cause clinically relevant drug-drug interactions mediated by CYP450 enzymes and the efflux transporters. However, concomitantly administered CYP3A4 inducers and inhibitors may affect the pharmacokinetics of sunitinib.

# **Product description:**

Physical description: Yellow to orange powder

Molecular weight: 532.57 Daltons

**Drug procurement:** Sunitinib will be supplied by Pfizer will be used for this study. Sunitinib malate is distributed by Pfizer as 12.5 mg, 25 mg, and 50 mg capsules with mannitol, croscarmellose sodium, povidone, and magnesium stearate. Each opaque plastic bottle contains 30 capsules

**Storage requirements:** Store at controlled room temperature (150 to 300 C), and protect from light.

**Stability:** The shelf life for the 12.5 mg capsule is 24 month. The shelf life for the 25 mg and 50 mg capsules is 36 months.

**Route of administration:** Oral. Sunitinib malate may be administered without regard to meals.

**Drug Accountability:** The investigator or designated study personnel are responsible for maintaining accurate dispensing records of the study drug. All study drugs must be accounted for, including study drug accidentally or deliberately destroyed. Under no circumstances will the investigator allow the investigational drug to be used other than as directed by the protocol. If appropriate, drug storage, drug dispensing, and drug accountability may be delegated to the pharmacy section of the investigative site.

**Drug Destruction:** At the completion of the study, there will be a final reconciliation of drug shipped, drug consumed, and drug remaining. This reconciliation will be logged on a drug reconciliation form, signed and dated. Any discrepancies noted will be investigated, resolved, and documented prior to return or destruction of unused study drug. Drug destroyed on site will be documented in the study files.

**Patient Care Implications**: A yellow discoloration of the skin area may result following direct contact with the capsules. Wash the exposed area with soap and water immediately.

**Potential Drug Interaction:** Sunitinib malate is metabolized primarily by liver enzymes, particularly CYP3A4. CYP3A4 inducers (e.g., rifampin, dexamethasone) and CYP3A4 inhibitors (e.g., grapefruit juice, ketoconazole) should be avoided, if possible. Rifampin lowers sunitinib

malate Cmax concentration by more than 2-fold. Ketoconazole increases sunitinib malate Cmax by 1.6 fold. Dose reduction with the CYP3A4 inhibitors is recommended, based on clinical symptoms. Concomitant treatment with dysrhythmic drugs, i.e., terfenadine, quinidine, procainamide, sotalol, probucol, bepridil, haloperidol, risperidone, and indapamide, is not recommended.

# 10.0 PATIENT REPORTED OUTCOMES (PROs – See Appendix #3)

#### 10.1 Quality of life (QOL) questionnaires

QOL questionnaires will be utilized to evaluate patient reported outcomes. This would include the Functional Assessment of Cancer Therapy- General (FACT-G) scale.

The Functional Assessment of Chronic Illness Therapy (FACIT) Measurement System is a collection of health-related quality of life (HRQOL) questionnaires targeted to the management of chronic illness [34]. The validated FACT-G scale is a 27-item compilation of general questions divided into four primary QOL domains: Physical Well-Being, Social/Family Well-Being, Emotional Well-Being, and Functional Well-Being. It is appropriate for use with patients with any form of cancer is widely used for assessing health-related QOL for different cancers. This questionnaire was designed for self-administration, written at 4th grade reading levels, and can be completed in 5-10 minutes [34]. A higher total score suggests well-being, and a lower score is an indication of inferior QOL.

#### 10.2 Rationale

With the availability of several new targeted agents that prolong survival in mRCC, there is increasing emphasis on patient preferences based on treatment related quality of life. Two recent randomized trials, COMPARZ and PISCES (pending publication), demonstrated differences in QOL amongst sunitinib and its active comparator, pazopanib [19, 20]. The impact of treatment related toxicities on patients' QOL while receiving sunitinib on the 2/1 schedule is thus an important end-point of interest.

#### 10.3 Data collection

QOL questionnaires will be administered at the initiation of treatment (baseline), and then at week 12, week 24 and week 36. These will be administered by the study team prior to patient encounters with the physician. The study team will also check for completion of all elements in each questionnaire, which will be collected from the patient at the end of that encounter. Only forms with more than 50% answers in each subscale will be considered acceptable. Moreover, at least 80% of questions overall in each questionnaire should be answered in order for it to be considered acceptable for analysis.

Missing data: Prorating subscale scores is acceptable as long as more than 50% of the items have been answered (e.g., a minimum of 4 of 7 items, 4 of 6 items, etc). The total (FACT-G) score is considered appropriate to score as long as overall item response rate is greater than 80% (e.g., at least 22 of 27 FACT-G items complete) [34].

#### 10.4 Data analyses

The end-point for all three PROs would be the mean score at each time point-baseline, week 12, week 24 and week 36. Descriptive summary statistics will be calculated for all continuous variables (means, standard deviations, medians, ranges, percentage of patients scoring in the highest category for each item) for the items in the subscales each time point. The mean trajectories of each group over time will be plotted for the total scores, along with scores for physical well-being, social well-being, emotional well-being and functional well-being-specific scales for FACT-G.

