<sup>9FACT-G to be administered at visits during baseline, week 12, week 24 and week 36 assessments prior to MD encounter. Study team to check for completion of QOL data: more than 50% questions in each subscale, and at least 80% of questions overall in each questionnaire should be answered for the questionnaire to be considered complete.

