# Subsequent cycles – each visit at Day 42

- The assessment and evaluation in subsequent visits will include all the items enlisted in cycle 2 day 42, except:
- Restaging scans that will be performed every even numbered cycle (cycle 4, 6, etc.)
- QOL questionnaires will be assessed at baseline, week 12, week 24 and week 36 only.
- Biological correlate: Serum, plasma, buffy coat samples will be collected at at baseline, week 12, week 24, week 36, and at the time of disease progression.
- Bone scan will be repeated in patients with bone metastases at baseline or at the development of signs/symptoms consistent with bone metastases.
- CT/MRI brain will not need to be repeated unless a patient was to develop clinical symptoms that warrant brain imaging, in which case the decision to conduct CT versus MRI of the brain will be at the discretion of the treating physician.
- TSH will be checked in every even numbered cycle and additionally if clinically indicated.

• After 12 cycles, labs and follow-up visits may be allowed every 12 weeks instead of every 6 weeks if clinically indicated at the discretion of the treating physician.

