# 16.2 Definition of secondary outcomes/endpoints:

- Progression-free survival (PFS) defined as the time from treatment initiation to disease progression using RECIST v 1 or death.
- Incidence of all ≥grade 3 toxicities per CTCAE version 4.03 criteria, defined as the percentage of patients who experience any grade 3 or greater toxicity that is possibly, probably, or definitely related to study therapy.
- Dose reductions, dose interruptions, dose delays will be recorded using pill diaries
  maintained by patients that will be reviewed and recorded at each visit. This outcome will be
  reported as the percentage of patients who underwent one or more dose reductions, dose
  interruptions and/or treatment delays. The number of patients who discontinue treatment due
  to unacceptable toxicities will be recorded, and reported as a percentage of the total number
  of enrolled patients.
- Changes in the patient reported outcomes in FACT-G (general) scale during treatment on schedule 2/1
- Changes in circulating DNA levels with antiangiogenic treatment
- Correlation of tumor associated macrophages (TAM) with response to therapy

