#### 16.5 Analytic plan for secondary objectives:

- PFS will be measured from the date of initiation of treatment to the first of documented progression or death; and will be estimated using the Kaplan-Meier method. PFS is expected to be comparable to that seen with 4/2 (11 month median); however if the upper bound of the interval is less than 8 months this will be taken as an indication that the efficacy of 2/1 is inferior to that of 4/2.
- Toxicities will be tabulated by type and grade, and the incidence of all  $\geq$  grade 3 toxicities will be calculated by CTCAE v 4.03 along with a 95% confidence interval
- The percentage of patients who underwent one or more dose reductions, dose interruptions and/or treatment delays will be estimated along with a 95% confidence interval. The number of patients who discontinue treatment due to unacceptable toxicities will be recorded, and reported as a percentage of the total number of enrolled patients along with 95% confidence interval.
- Health-related quality of life (HRQOL) will be assessed by FACT-G questionnaires as a secondary endpoint. Questionnaires will be administered at baseline, week 12, week 24 and week 36. Descriptive summary statistics will be calculated for all continuous variables (means, standard deviations, medians, ranges, percentage of patients scoring in the highest category for each item) for the items in the subscales each time point. The mean trajectories of each group over time will be plotted for the total scores, along with scores for physical well-being, emotional well-being, functional well-being, and renal-specific scales for FACT-G.

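### FACT-G is defined as change during treatment but analysed as raw means per visit, which mixes within-patient change with selective drop-out

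*Combined protocol and SAP*

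**What the plan says.** Section 16.2 lists as a secondary endpoint "Changes in the patient reported outcomes in FACT-G (general) scale during treatment". Section 10.4 sets the analysed quantity as the "mean score at each time point-baseline, week 12, week 24 and week 36" and adds that "The mean trajectories of each group over time will be plotted for the total scores" and for the subscales. Section 16.5 repeats this: "Descriptive summary statistics will be calculated for all continuous variables", followed by the same kind of plot. Neither section specifies a paired change, a longitudinal model or a count of forms per visit.

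On timing, section 12.2 says "QOL questionnaires will be assessed at baseline, week 12, week 24 and week 36 only", and the footnote to the study calendar (section 3.2) agrees: "FACT-G to be administered at visits during baseline, week 12, week 24 and week 36 assessments". FACT-G is not listed at the End of Treatment visit or the 30-day follow-up visit.

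On missing data, section 10.3 deals with unanswered items within a returned form: "Prorating subscale scores is acceptable as long as more than 50% of the items have been answered". It gives no rule for a patient who returns no form.

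On content, section 10.1 describes FACT-G as 27 items in four domains: physical, social/family, emotional and functional. Section 10.4 lists all four. Section 16.5 leaves out social well-being and adds "renal-specific scales for FACT-G".

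**The concern.** The endpoint and its analysis are different quantities. The baseline mean uses every patient with a form. The week-36 mean uses those still on treatment and attending. The difference between the two combines two things: how individual patients changed, and who is left.

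Patients leave for progression or unacceptable toxicity (sections 3.1 and 6.3), and either may go with a poorer score. There is one arm, so baseline is the only comparison and no control group shares the attrition. Section 10.2 gives quality of life on the 2/1 schedule real weight. As planned, a flat or rising curve could not be told apart from the effect of lower-scoring patients leaving.

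**Working it through.** The plan gives no numerical target for FACT-G, so there is none to reproduce. The check asks how many forms could be missing and how far that could move a raw mean.

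**Inputs from the plan.** 60 patients (16.3); 11-month median PFS expected (16.5); forms at baseline and weeks 12, 24 and 36 (10.3).

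**Assumptions.** Exponential PFS; 30.44 days per month; treatment stops at progression; a baseline gap of 4 to 10 points between stayers and leavers, for which the documents give no figure.

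**Step 1: progression by week w.** Share progressed = 1 − 0.5^((7w/30.44)/11).
- Week 12: 16.0%, leaving 50.4 of 60
- Week 24: 29.4%, leaving 42.4 of 60
- Week 36: 40.6%, leaving 35.6 of 60

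**Step 2: forms missing at week 36.** If everyone who has progressed by week 36 gives no form, 41% are missing. However, restaging and FACT-G fall at the same Day 42 visit of even cycles, and the form is completed before the physician is seen. A patient whose progression is first found at the week-36 scan would normally still complete that day's form. The missing forms then come from those who had progressed by week 24, which is 29%. The range is 29% to 41% before toxicity withdrawals. For illustration, adding an assumed 10% or 20% toxicity withdrawal by week 36 to the 41% case leaves about 32 or 29 of 60.

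**Step 3: shift in the raw mean when nobody changes.** Let m be the share missing, S the stayers' baseline mean and L the leavers'. The full baseline mean is (1 − m)S + mL. The later mean is S. The difference is m(S − L).

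| Baseline gap S − L (assumed) | m = 0.294 | m = 0.406 |
|---|---|---|
| 4 points | 1.2 | 1.6 |
| 6 points | 1.8 | 2.4 |
| 8 points | 2.4 | 3.3 |
| 10 points | 2.9 | 4.1 |

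With a gap of zero the shift is zero.

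**Step 4: what paired change recovers.** A simulation of 400,000 patients used the 41% loss, with an assumed total-score SD of 15, within-patient correlation of 0.6, and drop-out depending on the patient's underlying level.
- No true change, drop-out odds ratio 1, 1.5, 2 or 3 per SD lower quality of life: the raw week-36 minus baseline difference is 0.0, +2.2, +3.4 or +4.7. Paired change is 0.0 throughout.
- True decline of 3 points, odds ratio 2: raw means show +0.4; paired change shows −3.0.
- The same mean decline, but patients also differ in rate of decline (assumed SD 4 points per 12 weeks): raw means show +1.7, paired change −1.1, against a true −3.0.

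Paired change therefore removes selection on a stable level, but not drop-out linked to decline itself.

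**The case against.** **The bias is possible, not shown.** A reader might infer that the planned curve is biased in favour of the 2/1 schedule. The documents do not support that. They give no FACT-G standard deviation, no leaver–stayer gap and no link between score and drop-out, and with unrelated drop-out the shift is zero. They also set no FACT-G comparator, threshold or test for a bias to act on. This objection stands.

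**The loss could be overstated.** A flat 41% counts patients who would normally complete the week-36 form on the day their progression is found. Section 6.3 also lets some patients continue past progression when they are clearly benefiting. This stands, and it is why a range is given. Deaths, clinical progression between scans and toxicity withdrawals push the other way. Continuation past progression also keeps patients who are doing well, so it does not remove the selection.

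**On-treatment quality of life is the stated target.** Sections 10.2 and 16.2 ask about patients while on the drug, so describing those patients is partly the aim. A reader might also infer that change is not described at all; that goes too far, since the plotted means do show change at group level. What remains is that a comparison of different sets of patients is not a change in patients.

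**The remedy is partial.** Neither paired change nor a mixed model fully handles drop-out driven by decline, as step 4 shows for paired change. This stands and is why a sensitivity analysis belongs in the fix.

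**The renal-scale point is editorial.** True, and the questionnaire in Appendix 3 should not be used to prove it, because the available text of that form is incomplete. The four-domain description in section 10.1 is enough.

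**Conclusion.** The mismatch between 16.2 and sections 10.4 and 16.5 is plain on the text and should be corrected. Its possible size at week 36 is a spurious rise of about 1.2 to 4.1 points. That rests on the plan's 11-month median PFS, exponential times, 29% to 41% of forms missing before toxicity withdrawals, and an assumed baseline gap of 4 to 10 points. With no link between drop-out and quality of life it is zero. Confidence is high on the wording and moderate on the size.

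The consequence is limited. FACT-G is one of six secondary objectives, is analysed descriptively and carries no decision rule. The primary toxicity analysis and its conclusion are unaffected. Separately, the subscale list in 16.5 is wrong as written.

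**What to change.** 1. In 10.4 and 16.5, make within-patient change from baseline at weeks 12, 24 and 36 the analysed quantity, for the total score and the four domains. Give a 95% confidence interval and the number of forms contributing at each visit.
2. Preferably estimate it from a repeated-measures model that keeps baseline in the outcome vector, so that patients with no later form still contribute. State the missing-at-random assumption.
3. Show baseline scores by last completed visit, so that selection can be seen directly. Keep the raw means as a supplement.
4. Add a simple sensitivity analysis for drop-out linked to decline, for example by lowering the unobserved later scores over a stated range.
5. In 16.5, delete the renal-specific scales and restore social well-being, to match 10.4 and 10.1. In 10.4, correct the references to three PROs and to groups, since there is one questionnaire and one arm.

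The cost is a wording change and one standard model on data already being collected. The small downside is an assumption about missing data that must be stated and tested. A FACT-G form at the existing End of Treatment visit would add information on leavers. It is optional, and section 10.1 puts completion at 5 to 10 minutes.
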